1. STUDY PROTOCOL

1.1. Objective and Study Design

This is a prospective, observational study designed to evaluate the impact of preoperative anxiety on postoperative early recovery parameters, pain intensity, and the development of emergence delirium in pediatric patients.

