1.5. Assessment and Data Collection

- **Preoperative Assessment:** Anxiety levels were assessed immediately before anesthesia induction using the Modified Yale Preoperative Anxiety Scale (mYPAS). Scores range from 23 to 100, with ge 30 indicating clinically significant anxiety.

- **Postoperative Assessment:** Conducted in the Post-Anesthesia Care Unit (PACU) at 0, 15, 30, 45, and 60 minutes:
 - **Pain Intensity:** Measured using the FLACC (Face, Legs, Activity, Cry, Consolability) scale (0–10).
 - **Emergence Delirium:** Monitored using the Pediatric Anesthesia Emergence Delirium (PAED) scale. Scores ≥ 10 indicated clinically significant delirium.
 - **Recovery Quality:** Evaluated using the Modified Aldrete Score (0–10).

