2. STATISTICAL ANALYSIS PLAN (SAP)

2.1. Sample Size and Power Analysis

Sample size was determined based on the positive correlation coefficient ($r = 0.479$, $P = 0.001$) between preoperative anxiety and postoperative pain scores reported in the literature. With a Type I error rate (α) of 0.05 and a power (1-beta) of 0.95, the minimum required sample size was calculated as 51 patients. The study was completed with 114 patients to account for potential data loss and clinical variations.

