2.2. Statistical Methodology

- **Data Distribution:** Assessed using the Shapiro-Wilk test.
- **Descriptive Statistics:** Continuous variables are presented as Mean \pm Standard Deviation or Median (Interquartile Range). Categorical variables are presented as frequencies and percentages (n, %).
- **Comparative Analysis:** * Independent samples t-test, Pearson Chi-square, or Fisher's Exact tests were used for demographic and clinical comparisons.
 - The Mann-Whitney U test was applied for comparing PAED, FLACC, and Aldrete scores between groups (mYPAS < 30 vs. mYPAS ≥ 30).
- **Risk Analysis:** Raw Odds Ratios (OR) and 95% Confidence Intervals (CI) were calculated for clinical risk assessments at specific time points.
- **Regression Modeling:** Multivariate Logistic Regression analysis using the "Enter" method was performed to determine the independent effect of preoperative anxiety on outcomes. Models were adjusted for age, sex, ASA score, surgical history, and surgery type.
- **Significance Level:** $p < 0.05$ was considered statistically significant for all analyses.

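### No child-level delirium event is defined across the five PAED readings, and odds ratios at single time points do not match the objective of development of delirium

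*Combined protocol and SAP*

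**What the plan says.** Section 1.1 gives the aim as the effect of preoperative anxiety on "postoperative early recovery parameters, pain intensity, and the development of emergence delirium in pediatric patients".

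Section 1.5 describes the postoperative assessments: "Conducted in the Post-Anesthesia Care Unit (PACU) at 0, 15, 30, 45, and 60 minutes". For PAED it adds a cut-off: "Scores ≥ 10 indicated clinically significant delirium". FLACC and the Aldrete score have a range but no cut-off.

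Section 2.2 contains three analyses that could bear on delirium:

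- Score comparison: "The Mann-Whitney U test was applied for comparing PAED, FLACC, and Aldrete scores between groups", with no time point or summary score named.
- Unadjusted odds ratios: "Raw Odds Ratios (OR) and 95% Confidence Intervals (CI) were calculated for clinical risk assessments at specific time points". Neither the time points nor the outcome is named.
- Adjusted logistic regression "to determine the independent effect of preoperative anxiety on outcomes". Neither the event nor the time point is named.

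No section mentions delirium at any reading, peak PAED, cumulative incidence or persistence.

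**The concern.** Developing delirium is a property of the child over the recovery stay. Being delirious at minute 30 is a property of that minute. It depends on whether delirium occurred and on how long it lasted. The plan states the first as its aim, and the only timing it gives for a binary analysis belongs to the second.

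Two things are at stake if a time-point odds ratio is reported as the delirium result. First, its no-event cell includes children who were delirious at another reading, so the delirium percentage can be too low. Second, onset and duration are mixed. If anxious children were only delirious for longer, a late odds ratio could be read as a higher risk of delirium. If their delirium came and went early, a late odds ratio would miss it.

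This is separate from multiplicity and from adjustment. One pre-chosen, adjusted time-point odds ratio would still answer a different question from the one in section 1.1.

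**Working it through.** **1. The plan's own figure.** The only calculation in the documents is the sample size in section 2.1: r = 0.479, α = 0.05, power 0.95, minimum 51. By Fisher's z, two-sided:

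n = ((1.960 + 1.645) / atanh(0.479))² + 3 = (3.605 / 0.5217)² + 3 = 50.75, rounded up to 51.

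It reproduces. It concerns the correlation "between preoperative anxiety and postoperative pain scores reported in the literature", so it gives no delirium rate.

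**2. The cut-off applied reading by reading.** These are three invented PAED records at 0, 15, 30, 45 and 60 minutes.

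| Child | PAED | ≥10 at 30 min | ≥10 at any reading |
|---|---|---|---|
| A | 4, 13, 8, 3, 1 | no | yes (15 min) |
| B | 12, 9, 5, 2, 0 | no | yes (0 min) |
| C | 2, 3, 2, 1, 0 | no | no |

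In a 30-minute table all three share the no-event cell. That is correct for minute 30 and wrong for development of delirium.

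**3. What holds without assumptions.** With p₁ to p₅ the proportions at or above 10 at each reading:

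max(pⱼ) ≤ P(any reading ≥10) ≤ min(1, Σpⱼ).

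A single-reading count can only equal or understate the any-time count. The share of ever-delirious children missed at reading j is 1 − pⱼ / P(any). It is zero if every case is present at that reading, for example at 0 minutes if delirium is always present then and only resolves.

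**4. Illustration with N = 114 (section 2.1) and assumed rates.** The documents give no delirium rates and no within-child correlation. The model is latent normal with a common correlation ρ between readings.

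- 20% at every reading, ρ = 0: P(any) = 1 − 0.8⁵ = 0.67. Missed: 1 − 0.20/0.67 = 70%. That is about 76 children ever delirious against 23 at one reading.
- Same rates, ρ = 0.6: P(any) = 0.45, missed 56%. At ρ = 0.9: P(any) = 0.31, missed 36%.
- Declining 30/20/10/5/2%, ρ = 0: P(any) = 1 − 0.7 × 0.8 × 0.9 × 0.95 × 0.98 = 0.53. Missed at 0 minutes 43%, at 60 minutes 96%. At ρ = 0.9: 7% and 94%.

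**5. Two-group illustration (simulated).** Assumed: 57 against 57 children; AR(1) latent scores with lag-one correlation 0.5–0.9; low-anxiety rates of 15/20/15/8/4% (profile 1) or 25/20/12/6/3% (profile 2); anxious group shifted by 0.5 SD at every reading; unadjusted chi-square test.

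| Outcome | Ever-delirious children missed | Power |
|---|---|---|
| 0 min | 13–57% | about 0.46–0.57 |
| 15 min | 19–48% | about 0.51–0.54 |
| 30 min | 36–66% | not tabulated |
| 45 min | 62–81% | not tabulated |
| 60 min | 79–90% | about 0.22–0.28 |
| Any reading | none | about 0.55–0.76 |

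Any-time incidence is 35–55%, against a highest single-minute prevalence of 28–34%.

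**6. Odds ratios in the same simulation.** At correlation 0.9 the any-time odds ratio is 2.32 (profile 1) and 2.28 (profile 2). The 0- and 15-minute values are 2.38 and 2.31 (profile 1), and 2.25 and 2.29 (profile 2). At correlation 0.5 the any-time values are 2.74 and 2.68, inside the single-minute ranges of 2.32–2.91 and 2.26–2.92. The difference has no fixed direction and is often small.

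**The case against.** A reader might infer that the plan miscounts delirium, classing children who were delirious at another minute as delirium-free. The documents do not support that. Section 1.5 gives a score threshold and is silent on how readings combine, and silence is not a rule. The odds-ratio sentence does not name delirium. FLACC and Aldrete are scored at the same minutes, although PAED is the only one with a cut-off and so the natural candidate for a binary analysis. The logistic regression also yields odds ratios, and its unstated outcome could be any-time delirium. So it cannot be said that no planned odds ratio addresses development of delirium.

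A time-point odds ratio is also a valid estimate of the odds of delirium at that minute. It misleads only if presented as the answer to section 1.1.

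The size is open to challenge too. Rates, correlation and group split are all assumed, and a constant shift at every reading favours the any-time outcome. At correlation 0.9 the any-time power is 0.56, against 0.51 and 0.55 at the best single minute in the two profiles. The large shares missed at 60 minutes matter only if that reading is taken as incidence.

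Finally, any-time PAED ≥10 is one of several defensible rules.

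All of this stands, and it limits the wording and the size. It does not supply the missing definition, and the regression cannot resolve the question while its outcome is unstated.

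**Conclusion.** The point holds as a mismatch and a gap. The aim is "the development of emergence delirium in pediatric patients", no child-level event is defined, and the only timing attached to a binary analysis is by time point. Certain without further data: a single-minute percentage equals or understates any-time incidence, and a single-minute odds ratio for delirium estimates something other than the odds of developing it. Not established: that delirium has been miscounted, or that the anxiety association is biased in a particular direction.

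The figures are illustrative, since the documents give no delirium rates, within-child correlation or group split. On those assumptions the any-time event gains power over the 0- or 15-minute reading, clearly when delirium is brief and only slightly when it persists. The change is worth making because it is cheap and aligns the analysis with the aim.

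**What to change.** In section 2.2, define one delirium outcome per child: PAED ≥10 at any valid PACU assessment from 0 to 60 minutes, equivalently peak PAED ≥10. Name it as the outcome of the main delirium odds ratio and of the adjusted logistic model. Keep time-point results as secondary, name the time points, and label them as point prevalence.

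The cost is SAP wording and one derived variable from readings already collected. The downside is that a peak over five readings is more sensitive to one stray high score. A sensitivity analysis requiring PAED ≥10 at two assessments, shown beside the main result, covers this.

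### The adjusted models are logistic, but FLACC and Aldrete have no defined event: the adjusted effect of anxiety on pain and recovery rests on an unstated cut-off or is not estimated at all.

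*Combined protocol and SAP*

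**What the plan says.** Section 1.1 sets three targets for the effect of preoperative anxiety: early recovery, pain and emergence delirium. Section 1.5 measures all three at five PACU readings (0, 15, 30, 45 and 60 minutes).

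- **Delirium (PAED):** an event rule is given: "Scores ≥ 10 indicated clinically significant delirium".
- **Recovery:** "Evaluated using the Modified Aldrete Score", with a 0–10 range and no event.
- **Pain (FLACC):** a 0–10 range and no event.

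Section 2.2 plans three kinds of outcome analysis:

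- Mann-Whitney U on the PAED, FLACC and Aldrete scores between mYPAS groups (<30 against ≥30), unadjusted.
- Raw odds ratios with 95% CIs at certain time points. Neither the events nor the times are named.
- A logistic regression by the Enter "method was performed to determine the independent effect of preoperative anxiety on outcomes", adjusted for age, sex, ASA score, surgical history and surgery type. No dependent variable, cut-off or reading time is named.

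The 0.05 threshold applies to every analysis, with no multiplicity control stated. Section 2.1 bases the sample size on a correlation between anxiety and pain scores, and reports that "The study was completed with 114 patients".

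**The concern.** An odds ratio or a binary logistic model needs a yes/no event. For pain and recovery the documents give none. In an observational study the adjusted model carries the claim of an independent effect, and here the only adjusted model is logistic. Two readings are open, and each leaves a gap.

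1. **Pain and recovery are in the models.** The plural outcomes and the stated objective suggest this. A cut-off must then have been used that the plan does not record, and an 11-point score is reduced to two categories. Pain, the outcome behind the sample size, is analysed less efficiently in its adjusted model than the sample-size calculation assumes.
2. **Pain and recovery are not in the models.** Their only comparison is then the unadjusted rank test, and two of the three objectives have no covariate-adjusted estimate.

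Under the first reading there is a further exposure. With the cut-off and the reading time both unwritten, the plan does not exclude choosing among several.

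**Working it through.** **Step 1. The plan's own figure.** Inputs from section 2.1: r = 0.479, alpha 0.05, power 0.95. With Fisher's z, two-sided:

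n = ((z₀.₉₇₅ + z₀.₉₅) / atanh(r))² + 3 = ((1.960 + 1.645) / 0.5217)² + 3 = 50.75, rounded up to 51.

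This matches the plan: "the minimum required sample size was calculated as 51 patients". At N = 114 the power for that correlation is Φ(0.5217 × √111 − 1.960) = 99.98%. The sample size is sound, but it is a calculation for two scores, not for a dichotomised event.

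**Step 2. Outcome against analysis.**

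| Outcome | Event in 1.5 | Unadjusted full-score test in 2.2 | Adjusted analysis in 2.2 |
|---|---|---|---|
| PAED | ≥10 | Mann-Whitney | Logistic, definable; reading time not named |
| FLACC | none | Mann-Whitney | Logistic on an unstated event, or none |
| Aldrete | none | Mann-Whitney | Logistic on an unstated event, or none |

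**Step 3. Power cost of a cut-off.** The documents give no score distribution or group split, so these are simulations under assumptions: N = 114 and a rounded normal score on 0–10, with Pearson chi-square after the cut-off against Mann-Whitney on the full score. The latter is asymptotically the score test of the proportional-odds model, so it stands in for the unadjusted form of that model.

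| Assumed effect | Score shape and split | Full score | Cut-off |
|---|---|---|---|
| 0.5 SD | mean 2, SD 2.3, 57/57 | 71.0% | 54.4% at ≥4; 19.2% at ≥7 |
| 0.5 SD | mean 4, SD 2.3, 57/57 | 72.3% | 53.5% at ≥4, 55.7% at ≥5; 32.5% at ≥2 |
| r = 0.479 | mean 3, SD 2.5, 57/57 or 84/30 | 97–99% | 79–93% at 3–5; 79–81% at 1; 59% and 26% at 7 |

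At 0.5 SD a central cut-off loses 71.0 − 54.4 = 16.6, 72.3 − 53.5 = 18.8 and 72.3 − 55.7 = 16.6 points. At r = 0.479 the loss at cut-offs 3–5 is roughly 5–20 points.

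**Step 4. False positives if a cut-off were picked from the results.** Same kind of simulation under the null, taking the smallest p over the candidate cut-offs:

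| Choice left open | False-positive rate |
|---|---|
| One fixed cut-off, one reading | 4.7–5.2% |
| Best of three adjacent cut-offs, one reading | 11–12% |
| Best of five cut-offs (1, 3, 4, 5, 7), one reading | 17–19% |
| Fixed cut-off, any of five readings (within-child correlation 0.5) | about 19–21% |
| Best of five cut-offs over five readings (correlation 0.5) | about 55–57% |

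The last row assumes that all 5 × 5 = 25 tests are run and the smallest p reported. Varying the within-child correlation from 0.2 to 0.8 moves it from about 63% to 49%. The row above it shows how much arises from the choice of reading alone, with no choice of cut-off. Only a FLACC-like score was simulated; Aldrete was not.

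**The case against.** The strongest reply has four parts.

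- **Nothing says FLACC or Aldrete was dichotomised.** PAED ≥10 at five readings would satisfy both the odds-ratio and the regression wording, and the regression is not expressly called binary. This stands, and it is why the point is put as two alternatives. It does not close the gap: on the PAED-only reading, pain and recovery have no adjusted estimate.
- **The full scores are already analysed.** This stands. Mann-Whitney keeps every FLACC and Aldrete value, so no information is lost in the unadjusted comparison. It does not supply an adjusted effect or an odds ratio.
- **At the documented effect, power remains adequate.** Largely so: at r = 0.479 a central cut-off still has 79–93%. The loss becomes severe only for a smaller effect or an extreme cut-off.
- **Naming the cut-off and time would be enough.** That would remove the ambiguity, but not the loss of information. A full-score model removes both.

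A reader might infer that cut-offs were picked after the results were seen, because section 2.1 already reports the completed sample. The documents do not support that. The past tense dates the text, not the choice of a cut-off, and a conventional value may simply have gone unwritten. Nor should the figure of 55–57% be read as this study's error rate: it is a worst case, it depends on an assumed correlation, and part of it is time-point multiplicity.

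**Conclusion.** The point holds as a gap in specification with a real but bounded cost. Of the three outcomes, only delirium has an event that fits the planned odds ratios and logistic models. For pain and recovery the adjusted analysis either rests on an unstated cut-off or is absent, and the documents do not let a reader tell which.

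If scores were cut, the cost in the affected analyses is roughly 15–20 points of power at an assumed 0.5 SD difference and roughly 5–20 points at r = 0.479 for a central cut-off. The unadjusted comparison is unaffected. Inflation of false positives is a hypothetical risk left open, not a finding: about 17–19% for the best of five cut-offs at one reading, and about 50–60% in the worst case over five readings, against about 19–20% with a fixed cut-off.

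These sizes rest on assumed score shapes, group splits and within-child correlation, none of which is in the documents. The gap itself rests on the text alone.

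**What to change.** In section 2.2:

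1. Make the adjusted analysis of FLACC and of Aldrete a proportional-odds (cumulative logit) model on the full score, with the same mYPAS term and the covariates already listed. Report a common odds ratio with its 95% CI.
2. State the timing: either one named reading, or all five readings with a child-level random effect or clustered standard errors.
3. Keep binary logistic regression for PAED ≥10, and say whether the event is at a named time or at any reading.
4. Label any odds ratio from a FLACC or Aldrete cut-off as descriptive, without a p-value.
5. Disclose that the model was specified after data collection.

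The data and covariates are already collected, and ordinal regression is available in standard packages. The costs are a check of the proportional-odds assumption (graphically, for example), re-running a completed analysis, and the disclosure in item 5.

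### The forced-entry logistic model has at most 9.5 events per slope on 114 children and no sparse-data method; Firth penalisation with event counts would be a cheap improvement

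*Combined protocol and SAP*

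**What the plan says.** The Regression Modeling bullet of SAP section 2.2 reads: "Multivariate Logistic Regression analysis using the 'Enter' method was performed to determine the independent effect of preoperative anxiety on outcomes". It continues: "Models were adjusted for age, sex, ASA score, surgical history, and surgery type". It gives no number of levels for surgery type, no penalisation, no rule for separation and no limit on model terms. It also does not say which binary outcome, or which assessment time, is modelled.

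The phrase about time belongs to a different bullet. Under Risk Analysis, unadjusted odds ratios "were calculated for clinical risk assessments at specific time points".

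Sample size is treated only in SAP section 2.1. It rests on a correlation between anxiety and pain and ends with: "The study was completed with 114 patients". No expected event rate or event count appears anywhere. The only outcome cut-off is the one for PAED in protocol section 1.5: "Scores ≥ 10 indicated clinically significant delirium". None is given for FLACC or Aldrete.

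**The concern.** The adjusted odds ratio is what the SAP relies on to call the effect of anxiety independent of the other factors. Ordinary maximum likelihood tends to push a non-null log odds ratio away from zero when there are few events for each coefficient. It has no finite solution when a combination of covariates predicts the outcome perfectly (separation). Forced entry keeps every term however sparse, and the study was not sized for this model. A reader who is given an adjusted odds ratio without its event count cannot tell whether the estimate is stable.

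**Working it through.** **1. The plan's own figure.** Section 2.1 gives r = 0.479, alpha 0.05, power 0.95 and a minimum of 51. By Fisher's z, N = ((1.96 + 1.645)/atanh(0.479))² + 3 = 50.75, rounded up to 51 (two-sided). The figure reproduces. Power for that correlation at 114 is above 0.999, but this says nothing about a logistic model with five adjusters.

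**2. Slopes.** Anxiety, age, sex, ASA score, surgical history and surgery type take at least 6 slopes. Four surgery types (an assumption) would make 5 + 3 = 8.

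**3. Ceiling on events.** Counting the smaller outcome class as events, the maximum is 114/2 = 57. Events per slope are then at most 57/6 = 9.5, or 57/8 = 7.1. This step needs no assumed event rate.

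**4. Simulations at n = 114.** Event rates, covariate mixes and anxiety prevalence are not in the documents and are assumed.

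- Set A: 60% anxious; sex 15/85; ASA II 20%; prior surgery 30%; surgery type 40/30/20/10%; true odds ratio 3; 1,500 replicates per rate.
- Set B: anxiety prevalence 50% or 75%; surgery type with 2 or 4 levels; ASA II 15%; less common sex 20%; surgical history 25%; true odds ratio 1, 2 or 3; 600 replicates per cell.
- Set C: a further check of ordinary and Firth fits.

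| Event rate | Events | Per slope (6 / 8 slopes) | Any term separates: A; B | Anxiety term separates: A; B |
|---|---|---|---|---|
| 5% | 5.7 | 0.95 / 0.7 | 90%; 58–93% | 35%; 10–53% |
| 10% | 11.4 | 1.9 / 1.4 | 60%; 19–63% | 10%; 1–30% |
| 20% | 22.8 | 3.8 / 2.9 | 14%; 2–17% | 0.6%; 0–8% |
| 30% | 34.2 | 5.7 / 4.3 | 4%; 0–4% | 0%; 0–1% |
| 50% | 57 | 9.5 / 7.1 | not run; 0–1% | not run; 0% |

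**5. Bias of the anxiety odds ratio at 20–50% events.**

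- True 3, ordinary fit: geometric mean 3.13–3.52 in set B and about 3.3–3.8 in set C; median 3.3 in set A at 20% and 30%. The overstatement runs from 3.13/3 = 1.04 to roughly 1.26 (1.26 × 3 = 3.78, the top of set C after rounding).
- True 3, Firth: 2.91–3.10 (B), 2.96–3.17 (C), median 2.9 (A, at 20% and 30%). In set C, Firth's root mean squared error was equal to or below that of the ordinary fit in every cell.
- True 2 (B): ordinary 2.06–2.27 (+3% to +13%); Firth 1.92–2.04.
- True 1 (B): ordinary 0.95–1.06, so no consistent upward bias.

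**6. At 5–10% events.** Among fits that did not separate, the ordinary estimate for a true 3 ranges from 1.55 to 3.67 (B), because the most extreme data sets drop out as separated. At 5%, Firth gives about 2.3–2.5 (A and C), and cells of set B include values from 2.0 to 2.8. Firth keeps the estimate finite but does not restore the missing information.

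**The case against.** Four stronger readings are tempting, and the case against them is good.

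- **That the adjusted model is run at single time points.** A reader might infer this from "were calculated for clinical risk assessments at specific time points", but those words describe the unadjusted odds ratios. The regression bullet names no time. Sparse late-time models are not excluded, but they are not stated either.
- **That the model will often separate.** This depends on an event rate that the documents do not give. It holds at about 10% events or fewer; from 20–30% upward separation is uncommon to rare. Many of the separations fall on a sparse covariate, driven by assumed rare cells, and the anxiety estimate then stays finite (median 3.0 at 10% events and 3.4 at 20%, under set A).
- **That the Wald intervals fail to cover.** Under set A, 95% Wald coverage for anxiety was 98/97/97/96% at 5/10/20/30% events; across set C it was 94–99%. At low rates the intervals are wide, and useless when anxiety separates, but they do not under-cover.
- **That large spurious findings will follow.** With true odds ratio 3 under set A, an estimate above 10 together with p < 0.05 occurred in 1/7.5/6.4/3.2% of runs at the same four rates. With no true effect, false positives were 1/3/5/5%, and an estimate above 10 with p < 0.05 occurred in at most 0.2%.

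All four objections stand. They do not touch the ceiling of 9.5 events per slope, the absence of any sparse-data method, or the overstatement of a real effect. Nor do the documents name a primary outcome, so this model should not be called the study's headline result.

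**Conclusion.** The concern holds in a limited form. The events-per-slope ceiling follows from the documents alone, taking one slope per named factor as the minimum. Everything else is conditional on assumed covariate mixes and event rates. At 20–50% events, a true odds ratio of 3 is overstated by roughly 4–26%, and a null effect is not consistently inflated. At about 10% events or fewer, some term separates in roughly 20–90% of fits and anxiety itself in about 1–50%. The stated method does not produce false positives, and its intervals are not shown to be invalid. A better method is available at almost no cost, and readers need the event counts to judge the result.

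**What to change.** In the Regression Modeling bullet of SAP section 2.2:

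1. Replace ordinary maximum likelihood with Firth-penalised logistic regression and profile-likelihood 95% confidence intervals.
2. Report the number of events beside each adjusted odds ratio.
3. State the binary outcome of each adjusted model. For delirium, use one outcome per child: any PAED of 10 or more from 0 to 60 minutes. This uses the plan's own cut-off and cannot give fewer positive children than any single time point.
4. State the coding of surgery type, and merge sparse categories without reference to outcomes.
5. Describe any model with about 5% events as imprecise.

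The cost is SAP wording and a rerun in standard software, with no extra patients or data. Estimates shrink modestly towards 1, and at about 5% events the penalised estimate is itself too low, as shown above. Since section 2.1 describes the study as already completed, the report should say whether the change was made after the outcomes had been seen.
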